7.4 Subgroups Used for Efficacy Analysis

For efficacy analyses the following subgroups will be defined:

- Age: < 65 years / ≥ 65 years
- Age: ≤ 75 years / > 75 years
- Prior therapy lines: ≤ median / > median (Note: median will be determined in total safety population)
- High risk cytogenetics: Yes / No
- Sex: Male / Female
- ISS: I or II / III
- Percentage of plasma cells in bone marrow at screening: < 60 / ≥ 60
- Subjects refractory to
 - Proteasome inhibitors (PIs) and Immunomodulatory Drugs (IMiDs)
 - any IMiDs only (not refractory to any PIs, but allowed to be refractory to any other previous drug)
 - any PIs only (not refractory to any IMiDs, but allowed to be refractory to any other previous drug)

- last prior treatment line Yes / No
- any prior treatment line Yes / No

8. STUDY SUBJECTS AND DEMOGRAPHICS

8.1 Disposition of Subjects and Withdrawals

All subjects who provide informed consent will be included in the database and will thus be accounted for in this study. Descriptive summaries of population data will be presented for the total population and the safety population and will include

- The frequency and percent of subjects in each study population
- The disposition of subjects including
 - number of subjects screened, who failed screening and who are eligible
 - number of subjects treated
 - number of subjects who completed 1st treatment cycle (subjects with number of cycles completed ≥ 1 , see definition in section 7.3.6)
 - number of subjects who completed of 2nd treatment cycle (subjects with number of cycles completed ≥ 2 , see definition in section 7.3.6)
 - number of subjects with at least one Cycle 3+ treatment
 - number of subjects who terminated the study
 - number of subjects still ongoing
- Study discontinuations for all subjects treated by reason (as specified in eCRF) (safety population only)
- time on study [months] and duration of treatment [months] (see definition in section 7.3.6)

Moreover, a listing of screening failures with corresponding reasons will be provided.

8.2 Protocol Non-compliances

Evaluability of subjects according to the definition of the DLT evaluable population is checked on an ongoing basis by the clinical study team of Premier Research. If a subject is non-evaluable, a new subject will be enrolled and will need to meet the definition for the DLT evaluable population before DMC review, to have the required number of DLT evaluable population subjects. The information that indicates why subjects are not evaluable together, with the reason for the exclusion from the DLT evaluable population, will be provided by the clinical study team to biostatistics before each DMC review.

For the final analyses, the DLT evaluable population will be defined according to the decisions for inclusion/exclusion at the time of the DMC meeting.

Exclusions from the other analysis populations will be checked programmatically according to the definition of the analysis population, but will be reviewed case-by-case before data release for final analysis.

Individual subjects with their reasons for exclusion from any analysis population will be listed.

The clinical non-compliance tracker will be displayed separately in the appendix of the clinical study report.

8.3 Demographics and Other Baseline Characteristics

Descriptive summaries of the demographic and other baseline characteristics will be completed for the safety population.

Descriptive summaries of demographic and other baseline conditions will include:

- Demographics (age [both as a continuous variable and as number of subjects aged < 65 and aged ≥ 65, aged ≤ 75 and aged > 75 as well as 18-64, 65-84 and ≥ 85 years], gender, race, height, weight at screening, body mass index [BMI])
- Medical history
- Disease staging based on Durie-Salmon (including subclassifications A and B) and on ISS Criteria
- Previous non-drug and drug treatment of multiple myeloma
- Time since first diagnosis of multiple myeloma [months]
- Cytogenetics of MM cells (bone marrow)
- DNA analysis of FcγRIIIa polymorphism (mucosal cheek swab)
- Concomitant medication

Medical History: Note that medical history will be coded with Medical Dictionary for Regulatory Activities (MedDRA Version 20.1, and updated to the newest version 23.0 for the follow-up analyses). Incidences of findings in medical history will be summarized by system organ class (SOC) and preferred term.

Disease Staging Based on Durie-Salmon (including subclassification A or B), *and on ISS Criteria:* Disease staging will be summarized descriptively by main classification (I/II/III) and by subclassification as applicable separately for both staging criteria.

Previous Non-Drug/Drug Treatment: Previous non-drug treatment will also be coded with MedDRA. The following groups will be defined for previous non-drug treatment: stem cell transplantation, radiotherapy, other. Incidences of previous non-drug treatments will be summarized by group.

Previous drug treatment will be coded using the WHO Drug Dictionary (March 2011, and updated to the newest version March 2020 for the follow-up analyses). Based on preferred term and coding levels of the WHO Drug Dictionary, previous drug treatments will be allocated to the following groups and subgroups:

- Group “Cytotoxic agents” with subgroups “Alkylating agents”, “Antimetabolites”, “Alkaloids”, “Anthracycline agents”, “Platinum compounds” and “Other cytotoxic compounds”
- Group “Other agents” with subgroups “Antibodies”, “Protein kinase inhibitors”, “Proteasome inhibitors”, “HDAC inhibitors”, “Interferons”, “Immunomodulatory drugs”,

“Glucocorticoids”, “Other antineoplastic agents”, “Other”

Incidences of previous drug treatments will be summarized by group, subgroup and agent.

Moreover the number of previous lines of therapy (as entered into the eCRF) will be summarized descriptively (summary statistics and frequency table). The frequency table will contain cumulative subcategories, i.e. number of subjects with $\geq x$ prior therapy lines, for all possible numbers x .

Best response under treatment and type of progression associated with each previous drug treatment will be included in listings.

Moreover, it will be determined for each previous drug treatment if the subject was refractory to the treatment (see section 7.3.1).

Incidences of previous drug treatments to which subjects were refractory will be summarized by group, subgroup and agent.

In addition, the rate of subjects who were refractory to the most recent drug treatment line and the rate of subjects who were double-refractory will be presented.

Time Since First Diagnosis of Multiple Myeloma [Months]: Time since first diagnosis will be measured from date of first diagnosis until Cycle 1 Day 1.

Cytogenetics of MM Cells (Bone Marrow): The frequency of translocations t(4;14) and t(14;16) and deletions Del13 and Del17p13 and other documented cytogenetic abnormalities (measured at screening or known from historical data) will be summarized descriptively in a frequency table (categories: yes/no/missing/not tested). Moreover, the table will contain frequencies for high risk evaluation (see section 7.3.1).

DNA Analysis of FcγRIIIa Polymorphism (Mucosal Cheek Swab): The frequency of each genotype (158FF, 158VF, 158VV, other, missing) will be summarized descriptively in a frequency table.

Concomitant Medication: All medications will be coded using the WHO Drug Dictionary (March 2011, and updated to the newest version March 2020 for the follow-up analyses). Incidences of concurrent medications will be summarized by Anatomical Therapeutic Chemical (ATC) level 2 and ATC level 4.

Concomitant medication is defined as a medication other than study drug that was administered during the treatment or follow-up period from day of first treatment up to the end of study.

Therefore entries of medications which were discontinued before start of treatment will be excluded from concomitant medication tables but will be included and flagged in the listings as previous medications.

If the start/stop dates of medication are partially or completely missing a medication will be assumed to be concomitant if it cannot be definitely shown that the medication was not administered during the treatment or follow-up period. Missing dates will not be replaced.

Thus, the following approach will be taken for exclusion from concomitant medication because of discontinuation before start of treatment:

- If stop day is missing but month is complete, medication will only be excluded from concomitant medication if stop month is before month of treatment start.
- If stop day and month are missing but year is complete, medication will only be excluded from concomitant medication if stop year is before year of treatment start.
- If stop date is completely missing and/or medication is specified as “ongoing”, medication will not be excluded

Anti-MM Treatments During Study: If a subject receives any anti-MM treatment other than the IMP(s) during study, it is regarded as protocol non-compliance. Introduction of new anti-MM treatment should result in exclusion of the subject from further study participation.

Subsequent Anti-MM Treatments: The first subsequent anti-MM treatment planned and the corresponding start date will be captured in the eCRF, for subjects included based on protocol amendment 6 or afterwards.

Subsequent anti-MM treatment will be presented in listings. Moreover, it will be taken into account for the derivation of efficacy endpoints (see section 7.3.3).

9. IMMUNOGENICITY, EFFICACY AND PHARMACODYNAMIC ANALYSES

This study will examine the immunogenicity, efficacy and pharmacodynamics of MOR03087. Formal planned analyses are described below. It may be necessary for additional exploratory analyses to be completed in this study after results from the planned analysis are completed, to assess continued study of MOR03087. Full details of additional analyses will be given in the CSR.

9.1 Immunogenicity Analysis

One of the primary endpoints is to evaluate the immunogenicity of MOR03087 in the Safety Population. Anti-MOR03087 antibodies will be determined by a central laboratory. The analysis will be based on both absolute numbers (number and percentage of subjects who develop anti-MOR03087 antibodies) and semiquantitative assessments (anti-MOR03087 antibody titer determination of confirmed positive samples).

The number and percentage of subjects who developed confirmed anti-MOR03087 antibodies during the study will be summarized descriptively. Rates will be calculated with respect to all subjects in the analysis group.

Exact 95%-confidence intervals will be provided for the rate of subjects who developed anti MOR03087 antibodies in combined presentations (see section 7.2).

Time to development of anti-MOR03087 antibodies [months] will be summarised descriptively using Kaplan-Meier estimates for the median, 25% quantile, and 75% quantile. 95%-confidence intervals for median, 25% quantile and 75% quantile will be provided in combined presentations.

Moreover the percentage of subjects having developed antibodies after 2, 4 and 6 months together with the corresponding 95%-confidence intervals will be estimated from the Kaplan-Meier curve for combined data.

Kaplan-Meier plots for time to development of anti-MOR03087 antibodies [months] will be provided for combined data.

Exact 95% confidence intervals and Kaplan-Meier analyses will not be produced if only very few subjects develop anti MOR03087 antibodies.

Also, if only a few subjects develop anti MOR03087 antibodies, quantitative assessments will only be presented in listings. Otherwise, summary tables may be added.

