	Following completion of Parts A-C (dose escalation of MOR03087 alone, bi-weekly and weekly, and weekly with DEX), the MTD and/or recommended dose will be confirmed in a minimum of 6 subjects. Following completion of Parts D and E (dose escalation of MOR03087 in combination with POM+DEX and in combination with LEN+DEX), the MTD and/or recommended dose in each part will be confirmed in a minimum of 6 subjects. The recommended doses for the confirmation cohorts will be determined after review of all available safety data from the corresponding dose-escalation portion of the study and based on the recommendation of the DMC. The recommended dose may be the MTD or a dose below the MTD.
	The other primary and secondary endpoints will be analyzed descriptively using summary statistics for continuous data and frequency tables for categorical data. The 95% confidence intervals will be presented for rates or means in the recommended dose group of each treatment arm where appropriate. Kaplan-Meier estimates will be used where applicable.

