## **15.3 ImmunogenicityAnalysis**

One of the primary objectives will be to evaluate the immunogenicity of MOR03087 in the Evaluable Population and the Safety Population. This analysis will be based on both absolute (number and percentage of subjects who develop anti-MOR03087 antibodies) and semi-quantitative (anti-MOR03087 antibody titer determination of confirmed positive samples) assessments.

The number and percentage of subjects who develop confirmed anti-MOR03087 antibodies will be summarized descriptively by treatment arm and dose level. Exact 95% confidence intervals will be provided for the rate of subjects who developed anti-MOR03087 antibodies in the recommended dose group of each treatment arm.

Time to development of anti-MOR0387 antibodies will be summarized descriptively by treatment arm and dose level using Kaplan-Meier estimates for the median, 25% quartile, and 75% quartile. If only a few subjects develop anti-MOR03087 antibodies, quantitative assessments will only be presented in listings. Otherwise, summary tables will also be provided.

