9.2 Efficacy Analysis

All efficacy analyses will be provided for the Safety Population and will be repeated for the Efficacy Evaluable Population.

Rates will be calculated for each response category (sCR, CR, VGPR, PR, MR, SD, PD, missing) by visit (for C3D1, C6D1, and C12D1). Moreover, the ORR (PR or better), the CBR (MR or better) and the DCR (SD or better) will be calculated by visit (see section 7.3.3.1). The corresponding number of subjects in each of these response categories and all rates will be summarized in a frequency table by visit.

For best overall response, frequencies will be calculated for each response category (sCR, CR, VGPR, PR, MR, SD, PD, NE). Moreover, the ORR (PR or better), CBR (MR or better) and the DCR (SD or better) will be calculated, based on BOR per subject (see section 7.3.3.2). The corresponding number of subjects in each of these response categories and all rates will be summarized in a frequency table. The exact Clopper-Pearson 95%-confidence intervals for ORR, CBR and DCR will also be shown in combined presentations.

The denominator for calculating the rates (rates by visit and best response rates) will be the total number of subjects within the corresponding analysis group. In the summary of rates by visit, all withdrawals and protocol non-compliances after start of new anti-MM therapy will be analyzed as missing for all visits after withdrawal, and the counts of missing observations will be included into the denominator.

Both TTP and PFS will be analyzed using Kaplan-Meier methods. Kaplan-Meier tables for PFS and TTP will contain number of subjects, number of subjects with an event (non-censored subjects), percentage of subjects with an event, median time [months], 25% and 75% quantile. The 95%-confidence intervals for median, 25% quantile and 75% quantile will be provided in combined presentations.

Moreover, the percentage of subjects having an event after 2, 4 and 6 months together with the corresponding 95%-confidence intervals will be retrieved from the Kaplan-Meier curve in combined presentations.

For PFS, the reason for censoring as stated in Table 3 will be tabulated together with reasons for discontinuation (based on study completion page) for patients who discontinued the study without a PFS event. This information will be included in the listings as well together with detailed information concerning AE term(s) leading to withdrawal.

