- If the start day and months are missing but the start year is complete, an AE will only be excluded from TEAEs if the start year is before the year of first treatment or if the start year is after the end year of the treatment-emergent period or if the stop date/time is before the start of first treatment.
- If the start date is completely missing, an AE will not be excluded from TEAEs unless the stop date/time is before the start of first treatment.

Time from first treatment to onset of AE [days] will be calculated for complete dates only and will be included in listings.

The TEAE grading will be determined by the investigators according to the NCI-CTC toxicity criteria. If a subject experiences a specific type of adverse event more than once, only the maximum grading will be considered in tables of TEAEs by grading when calculating the incidences (number and percentage of subjects with AE of specific type and grade).

One of the primary endpoints will be to determine the incidence and severity of AEs.

A TEAE summary table will be presented showing the incidence and frequency of all

- Treatment-emergent AEs (TEAEs)
- TEAEs by grading (according to NCI-CTCAE toxicity criteria)
- TEAEs with Grade ≥ 3
- TEAEs with Grade 1 and 2
- TEAEs with Grade 3 and 4
- TEAEs related to MOR03087 / Pomalidomide / Lenalidomide / Dexamethasone
- Serious adverse events (SAEs)
- Serious adverse events (SAEs) related to MOR03087 / Pomalidomide / Lenalidomide / Dexamethasone
- MOR03087-related TEAEs by grading (according to NCI-CTCAE toxicity criteria)
- Pomalidomide-related TEAEs by grading (according to NCI-CTCAE toxicity criteria)
- Lenalidomide-related TEAEs by grading (according to NCI-CTCAE toxicity criteria)
- Dexamethasone-related TEAEs by grading (according to NCI-CTCAE toxicity criteria)
- DLTs
- Infusion reactions
- TEAEs leading to any action on MOR03087 / Pomalidomide / Lenalidomide / Dexamethasone
- TEAEs leading to withdrawal of MOR03087 / Pomalidomide / Lenalidomide / Dexamethasone

- TEAEs that caused the subject to withdraw from the study
- Symptomatic overdoses reported as TEAE

The incidence refers to the number and percentage of subjects with at least 1 TEAE of the specified type and the frequency to the number and percentage of AEs.

Exact 95%-confidence intervals for the incidence rates will be included in the summary tables for the combined data.

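### SAP 9.1 drops the exact 95% interval for the antibody rate, a primary endpoint, at an undefined low count; protocol 15.3 has no such exception (minor)

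*SAP*

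**What the plan says.** Both documents list immunogenicity as primary endpoint 4. It has an absolute part (how many subjects develop antibodies, and what percentage) and a semi-quantitative part (titers of confirmed positive samples).

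- **SAP 9.1, commitment.** "The number and percentage of subjects who developed confirmed anti-MOR03087 antibodies during the study will be summarized descriptively". It adds: "Exact 95%-confidence intervals will be provided for the rate of subjects who developed anti MOR03087 antibodies in combined presentations". SAP 7.2 defines combined presentations as tables by part (A to E) and tables of recommended dose data by part (C, D and E).
- **SAP 9.1, exception.** "Exact 95% confidence intervals and Kaplan-Meier analyses will not be produced if only very few subjects develop anti MOR03087 antibodies". A separate sentence then sends quantitative assessments to listings if only a few subjects are positive.
- **Protocol 15.3.** "Exact 95% confidence intervals will be provided for the rate of subjects who developed anti-MOR03087 antibodies", in the recommended dose group of each arm. Its only low-count clause is: "If only a few subjects develop anti-MOR03087 antibodies, quantitative assessments will only be presented in listings".
- **Protocol synopsis.** The general statement is softer: "95% confidence intervals will be presented for rates or means in the recommended dose group of each treatment arm where appropriate".
- **Other exact intervals in the SAP.** Section 9.2: "The exact Clopper-Pearson 95%-confidence intervals for ORR, CBR and DCR will also be shown in combined presentations". Section 10.2: "Exact 95%-confidence intervals for the incidence rates will be included in the summary tables for the combined data". Neither has a low-count condition.

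**The concern.** The SAP states a rule that removes a planned interval for a primary endpoint, and nobody could apply that rule the same way twice. The readable text gives no count, no proportion and no reference group. SAP 3.4 says that no personnel are blinded, so whether the interval appears would be settled with the counts in view.

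The rule also takes effect where the interval tells the reader most. With zero or one positive in a small group, the point estimate says little and the upper limit carries the information. A bare 0% can look like evidence of low immunogenicity when the data leave a substantial rate open. The same report would show exact intervals for equally sparse adverse events in the same groups.

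**Working it through.** **1. Is the exception already in the protocol?** Protocol 15.3 applies its few-positives clause to quantitative assessments. The endpoint definition sets the absolute part (number and percentage) apart from the semi-quantitative part (titers), so the clause reads most naturally as being about titers. SAP 9.1 supports this reading: it repeats the quantitative clause in its own sentence, after the sentence that drops the intervals. The interval exception is therefore new in the SAP.

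**2. Is there another reason for it?** Small groups are already dealt with in SAP 7.2, which limits 95% intervals to combined presentations because dose levels hold few subjects. An exact binomial interval can be computed at any count, including zero.

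**3. The plan's own figure.** Protocol 15.9 takes at least 9 subjects per recommended dose group and gives the chance of seeing an event at least once:
- 1 − (1 − 0.17)^9 = 0.813, stated as 81%.
- 1 − (1 − 0.23)^9 = 0.905, stated as 90%.

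Both reproduce. The complements are the chances of no event in 9: 0.187 at a true rate of 17% and 0.095 at 23%. They show that zero positives is a realistic result when the true rate is not small. They do not measure the effect of omitting the interval.

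**4. The limits that would be omitted.** Two assumptions: a two-sided 95% level, and the Clopper-Pearson method (SAP 9.1 says only exact; SAP 9.2 names Clopper-Pearson for response rates). With zero positives the upper limit is 1 − 0.025^(1/n).

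| n | Source of n | Upper limit at 0/n |
|---|---|---|
| 9 | Minimum recommended dose group: 6 + 3 (protocol 15.9, SAP 5) | 1 − 0.025^(1/9) = 33.6% |
| 12 | Assumed: 6 confirmation subjects + escalation cohort expanded to 6 | 26.5% |
| 18 | Planned maximum of Part B, D or E (synopsis) | 18.5% |
| 24 | Planned maximum of Part C (synopsis) | 14.2% |
| 48 | Planned maximum of Part A (synopsis) | 7.4% |

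With one positive the upper limit is the 97.5% quantile of a beta distribution with parameters x + 1 and n − x. That gives 48.2% for 1/9 and 38.5% for 1/12.

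**5. Per group or study-wide?** If the condition is judged per group, some parts could show the interval and others not. If it is judged over the study (up to 126 subjects), a handful of positives would remove every interval at once. SAP 9.1 allows either reading. The table shows what is lost in a group with no positives, whichever reading triggers the omission.

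**The case against.** The strongest objection is that little is lost. The number and percentage are reported in every case, individual values are listed, and the exact interval is a fixed function of x and n that any reader can compute. The analysis is descriptive, and no test or dose decision uses the antibody rate; the MTD rests on dose-limiting toxicities. All of this stands, and it sets the severity.

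The conflict with the protocol is also less sharp than section 15.3 alone suggests. The synopsis promises intervals only where appropriate, and 15.3 itself uses an unquantified few. Protocol 15.13 requires departures from the planned analysis to be described with reasons in the study report, so an omission should not be silent. These points stand in part. The synopsis leaves discretion but does not tie it to a low count, and the specific section gives the interval without that exception.

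The limits in the table also need a caveat. SAP 9.1 computes rates over all subjects in the analysis group, so subjects without an evaluable antibody result stay in the denominator. The figures hold as stated only if every subject was evaluable.

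Three stronger readings are tempting, and the documents do not support them:
- **That the primary endpoint goes unreported.** It does not; only the interval and the Kaplan-Meier output are dropped.
- **That the interval will be missing from groups of 9.** This assumes a per-group trigger and a particular meaning of very few, neither of which is stated.
- **That the clause is there to hide an unfavourable result.** Nothing in the text indicates this.

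**Conclusion.** The point holds as a minor reporting defect. SAP 9.1 adds an unquantified low-count exception to an interval that protocol 15.3 provides without one, and the SAP applies no such exception to comparable exact intervals. With no positives, the upper limit left out would range from 33.6% (n = 9) to 7.4% (n = 48).

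This rests on the assumptions above: Clopper-Pearson, two-sided 95%, all subjects evaluable, parts enrolled to their planned maxima for n = 18, 24 and 48, and an expanded escalation cohort for n = 12. The documents give no antibody counts, so whether the clause would ever be triggered is unknown. The planned table descriptions are redacted and could contain a threshold. That would settle the missing number but not the departure from protocol 15.3.

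**What to change.** In SAP 9.1, delete the very-few condition as it applies to the exact interval. State that the exact 95% interval for the antibody rate is printed in all combined presentations, including when the count is zero. The condition may stay for the Kaplan-Meier analyses, where very few events make quartile estimates uninformative. Because protocol 15.3 plans that summary too, an omission there should be recorded under protocol 15.13.

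This is one wording change. It needs no new data and brings the interval back into line with protocol 15.3. The cost is that small groups will show wide intervals.
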